7.9.2 Clinical Laboratory Parameters

For each quantitative clinical laboratory parameter (including Hemoglobin A1c, fasting blood glucose, and serum insulin) descriptive statistics of the observed values as well as change from study baseline will be presented overall for each assessment timepoint. Change from time-matched baseline will also be presented for fasting blood glucose, and serum insulin by cycle group.

Parameter values will also be categorized as low, normal, or high based on reference ranges provided by the lab, and shifts from baseline to each later timepoint will be tabulated. If there is more than one measurement for a lab parameter at a postbaseline timepoint, only the last measurement will be used.

Individual patient plots of fasting blood glucose and serum insulin values will be plotted over time as patients escalate from placebo through the IW-1973 doses.

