## STUDY SCHEMATIC

### SCHEDULE OF EVENTS

Visit Days → Study Procedure ↓	Screening Period	Clinic Period					Follow-up Period	
	Screening Visit (Day -28 to -2)	Check-in Day -1	1st day of cycle Days 1, 4, 7, 10, 13, 16	2nd day of cycle Days 2, 5, 8, 11, 14, 17	3rd day of cycle Days 3, 6, 9, 12, 15, 18	Discharge Day 19	Follow-up Visit Day 32 (± 2 days)	End of Trial Visit Day 46 (± 3 days)
Informed consent signed	X							
Inclusion/exclusion evaluation	X	X						
Demographics	X							
Medical history	X							
Physical exam	X	X				X		X
HBsAg, HCV & HIV screen	X							
Drug & alcohol screen (a)	X	X					X	
Pregnancy test (b)	X	X					X	X
Weight (W) & height (H) (c)	W, H	W	W			W	W	W
12-lead ECG (d)	X	X	pre: 0 (≤ 15m) pd: 1, 4h (± 15m)			X		
Respiratory rate & oral temp (e)	X	X				X	preNG: 0 (≤ 15m)	X
Clinical chemistry, coagulation, hematology, urinalysis (f)	X	X				X	preEndoPAT (≥1h)	
Hemoglobin A1c	X	X				X	preEndoPAT (≥1h)	
Fasting blood glucose & serum insulin (g)	X	X		pre: 0 (≤15m)		X	preEndoPAT (≥1h)	
Adverse event evaluations	X	X	X	X	X	X	X	X
Prior & concomitant meds	X	X	X	X	X	X	X	X
EndoPAT (h)	X	X			pre: 0 (≤ 1h) pd: 4, 12h (±15m)		preNG: 0 (≤ 1h) pdNG: 45m(±15m)	
Supine/standing BP & pulse supine only (i)	X		pre: 0 (≤ 30m) pd: 1,2,4,8,12h (±10m)		Supine only pre: 0 (≤ 30m) pd: 1,2,8h (±10m)	24h (± 15m)	Supine only preNG: 0 (≤ 30m) pdNG: 2h (+30m)	

Visit Days → Study Procedure ↓	Screening Period	Clinic Period					Follow-up Period	
	Screening Visit (Day -28 to -2)	Check-in Day -1	1 st day of cycle Days 1, 4, 7, 10, 13, 16	2 nd day of cycle Days 2, 5, 8, 11, 14, 17	3 rd day of cycle Days 3, 6, 9, 12, 15, 18	Discharge Day 19	Follow-up Visit Day 32 (± 2 days)	End of Trial Visit Day 46 (± 3 days)
[REDACTED]								
Platelet function (k)			pre: 0 (≤ 15m) pd: 4h (± 15m)					
Pharmacokinetic samples (l)			pre: 0 (≤ 15m) pd: 1,3,6,12h (± 5m)	pre: 0 (≤15m)		24h (± 15m)	preEndoPAT (≥1h)	X
[REDACTED]			[REDACTED]			[REDACTED]	[REDACTED]	[REDACTED]
[REDACTED]			[REDACTED]			[REDACTED]	[REDACTED]	[REDACTED]
Study drug administration (o)			X	X	X			
Ambulatory BP monitoring				Start: pre 0(≤30m) End: pd12h(+30m)				
Confined to clinic		X	X	X	X			
Discharge from clinic						X		
Nitroglycerin administration (p)							X	
Study completion								X

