### **3.4.3 Replacement Procedures**

Patients withdrawing from the study after first dose will not be replaced.

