### **3.6 STOPPING CRITERIA**

All dosing will be stopped if the Sponsor and Investigator determine that any of the following have occurred:

- Drug-related SAEs in 2 or more patients (per causality and SAE definitions in the protocol)
- An overall pattern of clinically significant AEs or an overall pattern of patient tolerability issues, which may appear minor in terms of an individual event but, in the opinion of the Sponsor or Investigator, collectively represents a safety concern

Note: Safety and tolerability will be assessed daily and dosing may be discontinued or dose escalation may be cancelled on an individual patient basis. Patients who discontinue dosing or do not escalate will remain in the clinic for at least 24 hours after their final dose of study drug and will complete all Discharge day assessments. In addition, these patients will return to the clinic for their Follow-up and End of Trial Visits 14 ( $\pm 2$ ) and 28 ( $\pm 3$ ) days, respectively, after their final dose of study drug.

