#### 3.9.3.4.2 Vital signs, ECGs, Clinical Laboratory Tests

Vital signs, 12-lead ECGs, clinical laboratory evaluations at each assessment timepoint and the change from study baseline (Day -1) at each postdose timepoint will be summarized by treatment group.

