4. DETERMINATION OF SAMPLE SIZE

The sample size in this trial was determined outside of statistical considerations. A sample size of 12 patients is considered sufficient and is based on precedent set by prior studies of similar nature.

**5. PHARMACOKINETIC, PHARMACODYNAMIC, AND
SAFETY ASSESSMENTS**

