7.9.4 ECG Parameters

For each ECG parameter, descriptive statistics will be presented by cycle group for each assessment timepoint. Change from study baseline (Day -1) statistics will also be presented for the predose assessment of each cycle. Shift tables from study baseline (Day -1) to the discharge visit (Day 19) for the overall ECG interpretation (normal, abnormal not clinically significant, or abnormal clinically significant) will be summarized for all subjects in the safety population. Change from time-matched baseline (placebo cycle) will be presented for QTc-F for each scheduled postdose assessment.

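### Discharge is the only full laboratory panel near dosing, but SAP 7.9.2 summarizes it without regard to the last dose received, a departure from the protocol that SAP 8 does not record

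*SAP*

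**What the plan says.** **When Discharge happens.** Protocol 3.6 says that "dosing may be discontinued or dose escalation may be cancelled on an individual patient basis". Such patients stay in the clinic for at least 24 hours after their final dose and "will complete all Discharge day assessments". The Synopsis says the same. Protocol 3.4.3 adds: "Patients withdrawing from the study after first dose will not be replaced".

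**What is collected.** In the Schedule of Events, chemistry, coagulation, hematology, urinalysis and HbA1c are taken at Screening, Check-in (Day -1), Discharge and Follow-up. The activity lists for the three cycle days (Protocol 3.8.2.2 to 3.8.2.4) contain none of them. Only fasting glucose and insulin are collected in every cycle, on its second day.

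**How it is to be summarized.**
- Protocol 3.9.3.4.2: "clinical laboratory evaluations at each assessment timepoint and the change from study baseline (Day -1) at each postdose timepoint will be summarized by treatment group".
- SAP 6.1 lists placebo and the five IW-1973 doses as the cycle groups for summary data.
- SAP 7.9.2, for every quantitative laboratory parameter: "descriptive statistics of the observed values as well as change from study baseline will be presented overall for each assessment timepoint". It adds results by cycle group for fasting glucose and insulin only. It also plans low/normal/high shift tables, without naming their grouping.
- SAP 7.9.4: "Shift tables from study baseline (Day -1) to the discharge visit (Day 19) for the overall ECG interpretation", for the whole Safety Population.
- SAP 8, which lists differences from the protocol, has no entry for the laboratory grouping. It does record that ECG change from study baseline is limited to predose assessments.

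**The concern.** Discharge is not tied to one dose. It is tied to each patient's final dose. A Discharge panel may follow placebo alone, 10 mg, or the complete escalation to 50 mg. Because these tests have no in-cycle collection, the last dose received is the only handle for relating them to treatment, and the overall layout removes it from the summary table.

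At stake is the reading of the one on-treatment safety panel in a study whose first objective is safety and tolerability. Patients who stop early may have tolerated the drug least. If their values enter one Discharge mean with those of patients who reached 50 mg, that mean describes no single exposure. A dose-related change at the top of the range would be diluted, and a change in a patient who stopped at a low dose would not be visible as such. The protocol's layout by treatment group would keep these apart.

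**Working it through.** The plan states no figure that bears on this. The sample size of 12 has no statistical derivation (SAP 4: "The sample size in this trial was determined outside of statistical considerations"), and no stopping rate is given. The check has three parts.

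**1. Which exposure can precede Discharge.** Inputs: six 3-day cycles over Days 1 to 18 (Protocol 3.1) and a stay of at least 24 hours after the final dose (Protocol 3.6). The earliest Discharge day is the last dosing day + 1.

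| Cycle of last dose | Dosing days | Earliest Discharge day |
|---|---|---|
| Placebo | 1–3 | 2–4 |
| 10 mg | 4–6 | 5–7 |
| 20 mg | 7–9 | 8–10 |
| 30 mg | 10–12 | 11–13 |
| 40 mg | 13–15 | 14–16 |
| 50 mg | 16–18 | 17–19 |

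If Discharge falls the day after the last dose, only a patient dosed through Day 18 has it on Day 19. Day 19 is therefore the nominal day for completers, not a property of the visit for everyone.

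**2. Whether early stopping is likely enough to plan for.** Protocol 3.5.2 says that 50 mg is above the maximum tolerated dose level in healthy volunteers. With an assumed stopping probability p per patient, independent across 12 patients, P(at least one) = 1 − (1 − p)^12.

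| Assumed p | P(at least one early stopper) |
|---|---|
| 5% | 1 − 0.95^12 = 46% |
| 10% | 1 − 0.90^12 = 72% |
| 20% | 1 − 0.80^12 = 93% |
| 30% | 1 − 0.70^12 = 99% |

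**3. What pooling would do to a mean.** Assume a laboratory change proportional to the last dose. If k of 12 patients stop at dose d and the rest reach 50 mg, the pooled mean as a fraction of the 50 mg effect is 1 − (k/12)(1 − d/50).

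| k | d = 10 mg | 20 mg | 30 mg | 40 mg |
|---|---|---|---|---|
| 1 | 0.933 | 0.950 | 0.967 | 0.983 |
| 2 | 0.867 | 0.900 | 0.933 | 0.967 |
| 3 | 0.800 | 0.850 | 0.900 | 0.950 |
| 4 | 0.733 | 0.800 | 0.867 | 0.933 |

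For example, with k = 4 at 30 mg, (8 × 50 + 4 × 30)/12 = 43.3, which is 87% of 50. With k = 0 the fraction is 1 and there is no effect. Both k and dose-proportionality are assumptions, so the table shows scale only.

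**The case against.** The strongest reply is that the limitation lies mostly in the design. There is one full panel after up to five sequential doses, and a completer's value follows all of them. A split by last dose sets completers beside self-selected stoppers, in cells that may hold one or two patients, and gives no unconfounded dose comparison. In a descriptive study an overall column is defensible. This stands as a limit on what the split can show. It does not explain why the protocol's grouping was dropped without an entry in SAP 8.

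Table specifications are in a separate document (SAP 1) that was not available. It might give early terminators their own row or column. Pooling is what the SAP text says as written, not a certainty about the final tables.

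The dilution concerns means. Shift tables count patients, so a stopper's abnormal value is not averaged away there.

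A reader might also infer three stronger things that the documents do not support:
- **That these labs cannot be read by dose at all.** SAP 9.1 lists all assessments, SAP 7.5 lists dosing and SAP 7.3 lists early terminators. With 12 patients, the last dose can be matched to the result by hand. Laboratory or ECG changes judged clinically significant or needing intervention are reported as AEs (Protocol 3.7.3.7), and TEAEs are assigned to the cycle of onset (SAP 7.9.1). Glucose and insulin are already shown by cycle group.
- **That early stoppers are excluded from the ECG shift table because their Discharge is not on Day 19.** Day 19 is the nominal visit label, and the table is stated to cover the whole Safety Population. The wording needs clarifying, but it does not exclude them.
- **That ECGs lack a summary by treatment.** SAP 7.9.4 gives descriptive statistics by cycle group. ECGs are taken predose and at 1 and 4 hours on the first day of each cycle, and QTcF change from the time-matched placebo value is planned.

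**Conclusion.** The point holds as a minor one that is cheap to correct. The laboratory grouping in SAP 7.9.2 differs from Protocol 3.9.3.4.2 and from the general layout in SAP 6.1, and SAP 8 does not record it. As written, it mixes last-dose levels in the only full panel near dosing. The SAP text has no rule that ties an early stopper's Discharge labs or ECG to the last dose, although it has such a rule for AEs.

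The size depends on events that the documents do not predict. It is zero if all 12 patients are dosed through Day 18. With 1 to 4 stoppers at 10 to 40 mg and a dose-proportional effect, the pooled mean would be 73% to 98% of the 50 mg effect. That range rests on assumption and is not evidence of harm. The patient listings allow a reading by dose, so the defect is in the planned summaries and their documentation, not in the data.

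**What to change.** - **SAP 7.9.2:** present Discharge laboratory results (change from Day -1 and shifts) by last dose received, including placebo, with an overall column.
- **SAP 7.9.4:** state that the Discharge ECG shift table uses each patient's own Discharge assessment after the final dose, and that Day 19 is only the nominal day for completers. Show the table by last dose received plus overall.
- **SAP 8:** record any departure from Protocol 3.9.3.4.2 that remains.
- **Table specifications:** check that the separate document uses the same rule.

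The cost is a few sentences and some table columns, with no new data or procedures. The drawback is small, self-selected cells. They should be read descriptively beside the overall column and not as a dose-response comparison.

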7.9.3 Vital Signs Parameters

Vital signs evaluations at each assessment timepoint not included in the PD analyses and the corresponding change from study baseline will be summarized for each cycle group.

The number and percentage of patients who had a notable change from baseline in BP and pulse (based on the criteria in Table 3), will be presented by cycle group.

Table 3. Criteria for Notable Changes in Post-Baseline Vital Signs

| Vital Sign Parameter | Flag | Criteria* | |
|---|-------------|-----------------------|-----------------------------------|
| | | Observed Value | Change from Study Baseline |
| Supine/Standing Systolic Blood Pressure (mmHg) | High | ≥ 180 | Increase of ≥ 30 |
| | Low | ≤ 90 | Decrease of ≥ 30 |
| Supine/Standing Diastolic Blood Pressure (mmHg) | High | ≥ 105 | Increase of ≥ 20 |
| | Low | ≤ 50 | Decrease of ≥ 20 |
| Supine Pulse Rate (bpm) | High | ≥ 110 | Increase of ≥ 20 |
| | Low | ≤ 50 | Decrease of ≥ 20 |
| Standing Pulse Rate (bpm) | High | ≥ 120 | Increase of ≥ 30 |
| | Low | ≤ 50 | Decrease of ≥ 20 |

*A postbaseline value is considered as a notable value if it meets both criteria for observed value and change from baseline.

The number and percentage of patients who meet the following criteria at any postdose timepoint will also be summarized by cycle group:

- Orthostatic decrease in systolic BP of > 20 mmHg from supine to standing
- Orthostatic decrease in diastolic BP of > 10 mmHg from supine to standing
- Orthostatic increase in pulse of > 20 beats per minute from supine to standing

7.9.4 ECG Parameters

For each ECG parameter, descriptive statistics will be presented by cycle group for each assessment timepoint. Change from study baseline (Day -1) statistics will also be presented for the predose assessment of each cycle. Shift tables from study baseline (Day -1) to the discharge visit (Day 19) for the overall ECG interpretation (normal, abnormal not clinically significant, or abnormal clinically significant) will be summarized for all subjects in the safety population. Change from time-matched baseline (placebo cycle) will be presented for QTc-F for each scheduled postdose assessment.

7.9.5 Other Parameters

7.9.5.1 Concomitant Medications

Any medication taken by patients after administration of study drug will be considered concomitant and presented in a data listing for the Safety Population.

7.9.5.2 Physical Examination

Physical examination results for all patients will be presented in a data listing for the Safety Population.

8. CHANGES IN THE CONDUCT OF THE STUDY OR PLANNED ANALYSES

The following analyses will be performed in addition to those described in the study protocol.

- Change from cycle baseline (defined as the assessment taken prior to drug administration at the beginning of each cycle) will be presented for cuff BP assessments (supine systolic BP, diastolic BP, and pulse), RHI assessments, and platelet function assessments.
- Change from trough baseline (defined as the last assessment prior to initiation of IW-1973 administration, that is, the Study Day 4 predose assessment) will be presented for trough supine systolic BP, diastolic BP, and pulse.
- Subgroup analyses by race (blacks vs. non-blacks) will be performed for daytime ABPM assessments and adverse events.
- Prevalent TEAEs in a cycle, defined as TEAEs that either started in or continued into a cycle, will be presented by SOC and PT for each cycle group using the Safety Population.
- Change from time-matched baseline (placebo cycle) will be presented for blood glucose, serum insulin and QTc-F for each scheduled postdose assessment.
- Change from study baseline in ECG assessments will be summarized only for the predose assessments in each cycle.

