### 3.8.2.2 First Day of Each 3-day Dosing Cycle (Days 1, 4, 7, 10, 13, 16)

- Weight
- 12-lead ECG predose ( $\leq 15$  minutes) and at 1 and 4 hours ( $\pm 15$  minutes) postdose
- Supine-to-standing (orthostatic) pulse and BP predose ( $\leq 30$  minutes) and at 1, 2, 4, 8, and 12 hours ( $\pm 10$  minutes) postdose
- PFA-100 test predose ( $\leq 15$  minutes) and at 4 hours ( $\pm 15$  minutes) postdose
- PK blood samples predose ( $\leq 15$  minutes) and at 1, 3, 6, and 12 hours ( $\pm 5$  minutes) postdose

- Administration of study drug and allowed concomitant medications
- Breakfast ( $\leq 30$  minutes) after study drug administration
- AE evaluation
- Concomitant medication recording

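### The SAP's ECG change from Day -1 stops before 50 mg: the Day 19 ECG has no planned numeric change, and the 50 mg column's value follows 40 mg (minor)

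*SAP*

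**What the plan says.** Protocol 3.9.3.4.2 covers vital signs, 12-lead ECGs and laboratory tests together and plans that "the change from study baseline (Day -1) at each postdose timepoint will be summarized by treatment group".

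SAP 7.9.4 is narrower for ECGs. It has four parts:

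- Observed values: "For each ECG parameter, descriptive statistics will be presented by cycle group for each assessment timepoint".
- Change from Day -1: "Change from study baseline (Day -1) statistics will also be presented for the predose assessment of each cycle".
- Day 19: "Shift tables from study baseline (Day -1) to the discharge visit (Day 19) for the overall ECG interpretation", with three categories (normal, and abnormal with or without clinical significance).
- QTcF: "Change from time-matched baseline (placebo cycle) will be presented for QTc-F for each scheduled postdose assessment".

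SAP 8 repeats the restriction: "Change from study baseline in ECG assessments will be summarized only for the predose assessments in each cycle". The sentence that opens that list reads "The following analyses will be performed in addition to those described in the study protocol". No reason is given for this item.

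The ECG schedule is in the Schedule of Events and Protocol 3.8.2.2 and 3.8.2.5. On the first day of each cycle there is a "12-lead ECG predose", then one at 1 h and one at 4 h. One more ECG is taken at Discharge on Day 19, with no clock time stated. SAP 6.1 presents summaries by cycle group, from placebo to 50 mg.

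**The concern.** Safety and tolerability is the first listed objective. Protocol 3.5.2 also acknowledges that 50 mg lies above the maximum that healthy volunteers tolerated on repeat dosing. ECG change at the top dose is therefore something a reader of the report will look for.

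Under the SAP, the change-from-Day -1 series uses only readings taken before the first dose of each cycle. Those readings reflect the previous cycle's dose. Two things follow. Nothing in the series reflects 50 mg. In a table by cycle group, the 50 mg column would show a reading taken after 40 mg, and a reader could take it for a 50 mg result.

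The one ECG that follows all three 50 mg doses is already scheduled, but it has no numeric change planned. Other Day 19 data are treated differently. SAP 7.9.2 gives laboratory parameters change from study baseline at each timepoint. SAP 7.7.1 gives supine BP and pulse a trough change that assigns the 24 h reading to the cycle just completed, so Day 19 counts as 50 mg.

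**Working it through.** The plan states no figure to reproduce. The check sets each scheduled ECG against the dosing calendar and the change analysis it receives.

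**Inputs.** Dosing (Protocol 3.1): placebo on Days 1–3, then 10, 20, 30, 40 and 50 mg for three days each, so 50 mg falls on Days 16, 17 and 18. ECG times and SAP rules are as above. Time-matched baseline (SAP 6.1) is defined for timepoints within the IW-1973 cycles that have a corresponding placebo-cycle assessment.

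| ECG day | Cycle group | Predose ECG follows | Change from Day -1 | Time-matched QTcF change |
|---|---|---|---|---|
| 1 | Placebo | no dose | predose | none (these are the baseline) |
| 4 | 10 mg | placebo | predose | 1 h, 4 h |
| 7 | 20 mg | 10 mg | predose | 1 h, 4 h |
| 10 | 30 mg | 20 mg | predose | 1 h, 4 h |
| 13 | 40 mg | 30 mg | predose | 1 h, 4 h |
| 16 | 50 mg | 40 mg | predose | 1 h, 4 h |
| 19 | Discharge | single ECG, after three 50 mg doses | none | none |

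**Counts per patient.**

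- Scheduled from Day 1: 6 × 3 + 1 = 19. Removing the Day 1 predose ECG leaves 18 after the first dose: 5 predose, 12 at 1 h or 4 h, and 1 on Day 19.
- Change from Day -1 kept by the SAP: 5 of 18. One of the 5 follows placebo; the other four follow 10, 20, 30 and 40 mg.
- ECGs after a 50 mg dose: 3 (Day 16 at 1 h and 4 h, and Day 19). Change from Day -1 is planned for 0 of 3. Numeric change of any kind is planned for 2 of 3 for QTcF and 0 of 3 for other ECG parameters.
- ECGs after any IW-1973 dose: 4 predose + 10 at 1 h or 4 h + 1 on Day 19 = 15. QTcF has some numeric change for 4 + 10 = 14 of 15, and the one left out is Day 19. Other parameters have it for 4 of 15.

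**Does the QTcF rule reach Day 19?** Its wording covers scheduled postdose assessments, but it needs a time-matched baseline. Day 19 is outside the cycles and no placebo-cycle ECG corresponds to it. The nearest match is the Day 4 predose ECG, about 24 h after the last placebo dose. That reading falls in the 10 mg cycle, and the SAP uses Day 4 predose as a trough baseline for supine BP and pulse only.

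**What observed summaries leave open.** They do not show the spread or the largest value of within-patient change. The difference between the Day 19 and Day -1 means equals the mean change only if the same patients contribute to both. Protocol 3.6 lets individual patients stop or not escalate, and 3.4.3 does not replace them. The documents give no ECG standard deviation, within-patient correlation or discontinuation rate, so the size of any distortion cannot be computed.

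**The case against.** The case on the other side is substantial, and most of it stands.

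- **The change is disclosed.** It appears in a section on changes to planned analyses and uses the word only. An inference that the SAP conceals the reduction is not supported. What remains is that the lead sentence misdescribes it and no reason is given.
- **Not every postdose change was lost.** A reader might count the twelve 1 h and 4 h readings plus Day 19 and conclude that none of 13 postdose ECGs keeps change from Day -1. That count is inconsistent. The predose ECGs on Days 4 to 16 are taken about 24 h after a dose, just as the Discharge ECG presumably is. Counted the same way, 5 of 18 keep it.
- **QTcF at 1 h and 4 h is well served.** Comparison with the same time in the placebo cycle is matched for time after dosing and for breakfast; the Day -1 ECG has no stated clock time. This is a sound replacement.
- **Much is covered elsewhere.** Observed values are summarised at each timepoint, all assessments are listed (SAP 9.1), and clinically significant ECG changes are reported as adverse events (Protocol 3.7.3.7). Heart rate is largely covered by supine and ambulatory pulse, including trough pulse after the last 50 mg dose. With 12 patients, individual changes can be worked out from the listings.
- **Table specifications are in a separate document** (SAP 1), so a Day 19 change row may exist there. The SAP text does not plan one, and the SAP 8 wording would exclude it.

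These arguments shrink the gap but do not close it. They do not supply a planned Day 19 change, and they do not correct the label on the Day 16 predose value.

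**Conclusion.** The point holds as a minor one. The SAP reduces a protocol-planned safety summary without a reason and under the wrong description. The remaining change-from-Day -1 series ends with a reading that follows 40 mg but belongs to the 50 mg cycle group. The Day 19 ECG is the only one after three 50 mg doses, and the only on-drug ECG with no planned QTcF change of any kind.

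This rests on two readings of the text: that ECG tables follow the SAP's cycle-group convention, and that the time-matched definition applies as written. It also takes all patients as reaching 50 mg. For a patient who stops early, the Discharge ECG follows a lower dose.

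A reader might infer that a QTcF signal at 50 mg would go unseen, or that the safety conclusions would be biased. The documents support neither. QTcF change is planned on Day 16 at 1 h and 4 h, observed Day 19 values are reported, inferential statistics are for description only, and the stopping criteria do not refer to this table. No distortion in milliseconds can be derived.

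**What to change.** 1. In SAP 7.9.4, add numeric change from Day -1 for the Discharge (Day 19) ECG, including QTcF. Label it by the last dose received, because patients who stop or do not escalate also complete the Discharge assessments.
2. Label the predose ECG change rows by the last dose received instead of the cycle about to start: Day 4 placebo, Day 7 10 mg, Day 10 20 mg, Day 13 30 mg, Day 16 40 mg. Day 1 follows no dose.
3. In SAP 8, state the predose-only rule as a reduction from Protocol 3.9.3.4.2, with its reason.
4. Optionally, extend the time-matched 1 h and 4 h change already planned for QTcF to the other ECG parameters. This is preferable to restoring change from Day -1 at those times.

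The cost is SAP wording and a few table rows. Every ECG needed is already scheduled, so no visit, procedure or patient is added.
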